Statistical Analysis Plan

Enhancing the QUality of psychological Interventions delivered by Telephone (EQUITy):

A cluster randomised trial of an 'enhanced telephone therapy' quality improvement intervention in NHS Talking Therapies

Short Title EQUITy

Trial Registration Number ISRCTN22583714

Protocol Version v11.0 (16/10/2023)

SAP Version v9.0 (21/07/2025)

Chief Investigator [name] (University of Manchester)

Health Economists [name] (University of Manchester)

[name] (University of Manchester)

Statisticians [name] (University of Manchester)

[name] (University of Manchester)

SAP Contributors [name] (University of Manchester)

[name] (University of Manchester)

Trial Design

The EQUITy trial is a two-arm, 1:1 allocation, cluster randomised, parallel-group, superiority trial (https://fundingawards.nihr.ac.uk/award/RP-PG-1016-20010). It compares Step 2 NHS Talking Therapies services (a cluster) receiving an 'enhanced telephone therapy' quality improvement intervention consisting of multiple components (service guidelines, team workshop and follow-up meetings; practitioner telephone training; resources for patients) with NHS Talking Therapies services following usual care.

The intervention has been developed to help NHS Talking Therapies services improve the quality of their telephone treatments. In the intervention clusters, staff will receive a team workshop, telephone training, educational materials to help patients understand treatments delivered by telephone and service guidelines to enhance practice. Patients will receive additional resources such as a leaflet introducing telephone treatment, an appointment card and a poster.

Patients in usual care will continue to receive routine NHS Talking Therapies care (routine telephone therapy).

Objectives

The primary objective is to assess the clinical effectiveness of the intervention:

Does the EQUITy intervention improve the mental health outcomes of patients compared to usual NHS Talking Therapies care?

A secondary objective relates to cost effectiveness:

Does the EQUITy intervention improve the cost-effectiveness of treatment compared to usual NHS Talking Therapies care?

Sample Size and Power

There are approximately 107 NHS Talking Therapies providers in England, and we aimed to recruit a minimum of 26 providers (clusters). With 13 clusters per arm, assuming an intracluster correlation (ICC) of 0.027 and a baseline-endpoint correlation (r) of 0.5, we would have 84% power to detect a standardised mean difference of 0.2 (at the 5% level of significance) assuming a minimum of 100 patients per provider.

However, by May 2024, it became apparent that we were not going to be able to meet the sample size of 26 clusters. There was also concern relating to the larger-than-expected variability in cluster sizes, which would affect study power via the large coefficient of variation. Subsequently, we decided that a fixed number of patients would be randomly selected from each provider. So long as this number is not less than 200 and the coefficient of variation in cluster size did not exceed 0.3, the study would retain at least 80% power to detect a standardised mean difference of 0.2 (with the ICC and r as above) with 22 clusters.

Randomisation

As a cluster trial, allocation to either the intervention or usual care took place at the provider level, via minimisation. The minimisation factors will be:

- NHS Talking Therapies clinical performance (Recovery Rate: % of annual NHS Talking Therapy referrals for persons aged 18+ finishing a course of treatment who are 'moving to recovery'; <52 vs. ≥52)
- Site size (count of NHS Talking Therapies patients receiving low-intensity therapy; <815 vs. ≥815)
- Use of telephone delivery (pre-pandemic); ≤33% vs. >33%
- Deprivation score (IMD); <20.8 vs. ≥20.8

Minimisation factor dichotomies were chosen in order that groups would be of roughly equal size, based on data available from NHS Talking Therapies services. Allocation was undertaken sequentially and independently by Manchester Clinical Trials Unit (CTU) to maintain concealment of allocation. A random weighting element of 4:1 allowed for allocation to the group which does not minimise the imbalance between minimisation factors (i.e. a 20% chance).

Outcome Assessment

The primary outcome measure will be the Patient Health Questionnaire (PHQ-9) for depression (Kroenke et al., 2001). The PHQ-9 will be collected at baseline and at the end of treatment, via routine NHS Talking Therapies data minimum data set.

The PHQ-9 is a 9-item measure of the severity of depression. Patients are asked how often they have been bothered by the nine symptoms of depression on a 4-point scale from 'not at all' (scoring 0) to 'nearly every day' (scoring 3). A total score, ranging from 0 to 27, indicates the overall severity of depression. Total scores of 5, 10, 15 and 20 represent cut-points for mild, moderate, moderately severe and severe depression, respectively.

The Generalised Anxiety Disorder (GAD-7) for anxiety (Spitzer et al., 2006) will be treated as a secondary outcome. The GAD-7 will be collected at baseline and at the end of treatment, via routine NHS Talking Therapies data minimum data set.

The GAD-7 is a 7-item measure of the severity of anxiety. Patients are asked how often they have been bothered by the seven symptoms of anxiety over the past two weeks. Responses are on a 4-point scale from 'not at all' (scoring 0) to 'nearly every day' (scoring 3). The GAD-7 total score ranges from 0 to 21. Total scores of 5, 10 and 15 are taken as cut-off points for mild, moderate and severe anxiety respectively.

Baseline Data

The NHS Talking Therapies minimum data set contains minimal patient covariates - age, sex, ethnicity and employment status. The completeness of the latter two varies between data sets and, as it is not viable to impute this type of information in the volume in which it is sometimes missing, they will not be used. Age and sex will be included in selected regression models (see *Inferential Analyses*).

Patient and/ or general practice postcodes are available either in part (e.g. M13) or in full and can be linked to the Index of Multiple Deprivation (IMD) at Lower Super Output Area level (as

per Stochl et al 2022). Where postcodes are only available 'in part', we will use a weighted average of all IMDs associated with such postcodes to derive the level of deprivation. NHS Talking Therapies service-level IMD has been used in the allocation process and so all models will include some control for this variable (along with the other minimisation factors).

Data on mode of intervention delivery (e.g. face-to-face, via telephone, etc.) are available and will be summarised for each treatment group separately. Data on treatment session attendance and/ or treatment completion will also be summarised by treatment group as appropriate (e.g. median; mode; range; % completing). Talking Therapies services define treatment completion as the attendance of at least two sessions recorded as either 'assessment and treatment' or 'treatment', followed by being discharged (https://www.england.nhs.uk/mental-health/adults/nhs-talking-therapies/service-standards/).

Statistical Analysis

Selection of Patients and Weighting

As per the amendment to the power calculation described earlier, for each cluster and separately for patients presenting with depression and anxiety, patients who are eligible to receive NHS Talking Therapies services will be ordered by their sex, age and date of first appointment. A simple random sample of 400 will then be drawn without replacement. Only patients whose baseline PHQ/ GAD, age and sex are not missing will be included in the sample (as it is unlikely that this information can be imputed accurately).

The sample with depression will be drawn first and 400 patients who present to each NHS Talking Therapy service (and are eligible for step 2 telephone-based psychological therapy) with mild, moderate or more severe depression (at baseline: i.e. $PHQ-9 \ge 5$) will be randomly selected to form an 'analysis sample'.

A second, non-overlapping, random sample of 400 patients with anxiety will be selected to analyse this outcome. Selection will also be based on patients who present to each NHS Talking Therapies service with mild, moderate or more severe anxiety (at baseline: i.e. GAD- $7 \ge 5$). If there are fewer than 400 patients identified for either sample, all such patients will be retained.

As NHS Talking Therapies service teams will see different numbers of patients, our primary approach will involve deriving probability weights (the inverse of the probability of being selected) in order that the patients selected at random better represent the wider population of patients seen by that particular team. We will also investigate unweighted analyses.

We have deliberately 'over-sampled' (400 patients) as it is not known what percentage of patients will not have engaged with their NHS Talking Therapies and, therefore, have missing outcome data (post-baseline). Although we will impute any missing 'end-of-treatment' PHQ-9/GAD-7 scores (defined as the last-recorded score, acknowledging that this may not be the end of treatment per-se), the reliability of such analyses is likely to decrease with increasing amounts of missing data. For example, if 50% of end-of-treatment PHQ-9/GAD-7 scores are not available, a complete case analysis will still retain 80% power to detect the desired effect.

Descriptive Analyses

As per CONSORT recommendations (Hopewell et al 2025), we will report the number of NHS Talking Therapies services approached and the number subsequently recruited and allocated

to each arm of the trial. Reasons for declining participation in the study will be noted. The number of eligible patients (the Talking Therapy service-level mean or median number, the range and the coefficient of variation), the number of eligible patients randomly selected from each Talking Therapy service and the number of randomly selected patients from each service who have outcome data at follow-up/ treatment completion (in each trial arm) will be reported.

Outcome variables (PHQ-9 and GAD-7) and model covariates (age, sex and, if sufficiently complete, ethnicity, employment status and level of deprivation) will be described, by trial arm, for the entire population of patients in our participating Talking Therapy services (at baseline only), all sampled participants (at baseline only) and the sub-sample (of sampled participants) who provide outcome data at follow-up (at baseline and follow-up) using (as appropriate) absolute frequency/ percentage, mean/ standard deviation, median/ interquartile range, minimum/ maximum and skewness/ kurtosis. The percentage of missing data will also be reported for each variable, overall and by treatment group. Data on mode of intervention delivery (frequency and percentage of each type), treatment session attendance and components of the intervention delivered will also be summarised.

Inferential Analyses

Null hypothesis: There is no significant difference in the severity of depression (primary)/ severity of anxiety (secondary) between patients receiving the 'enhanced telephone therapy' intervention and patients receiving usual care from NHS Talking Therapies services at the conclusion of their treatment.

Analysis Method: Analyses will be conducted using Stata (Vers.14 or later, StataCorp 2015) or R statistical software. Statistical tests will be performed with a 2-sided type I error rate of 5%. Patients will be analysed according to the trial arm to which their cluster was allocated (intention-to-treat). The analyses will be conducted following completion of treatment. It is possible that a number of patients in the database will not have completed their treatment. However, we will not know if this is the case. Therefore, we will analyse the last available data point as if it was their end of treatment. Although it may not be, this should not introduce any bias between arms.

Data on the outcome measures will be assumed to be continuous; multivariable mixed effects linear regression will be conducted (with the last recorded PHQ-9 score or the last recorded GAD-7 score as the dependent variable and the corresponding baseline values as a fixed effect covariate).

Models to be fitted: The following models will be reported. All models will include the minimisation factors and the specified covariates as fixed effects. For each proposed model, the number of participants with observed data for all variables included in the model will be reported. We will also report the adjusted difference in follow-up PHQ-9/ GAD-7 scores between trial arms (i.e. the regression parameter for trial arm), along with its 95% confidence interval and corresponding p-value.

Outcome	Model	Covariate(s)
PHQ-9/ GAD-7 at the end of treatment	0	Trial Arm Allocation only
	Α	Trial Arm Allocation
		PHQ-9/ GAD-7 at baseline
	B1 (all participants:	Trial Arm Allocation
	primary analysis	PHQ-9/ GAD-7 at baseline
	model)	Age and Sex

	B2 (subset of	Trial Arm Allocation
	participants,	PHQ-9/ GAD-7 at baseline
	equivalent to C)	Age and Sex
	С	Trial Arm Allocation
		PHQ-9/ GAD-7 at baseline
		Age and Sex
		Any Other Usable Variables *

^{*} We will investigate the data completeness of Employment Status and Ethnicity. We will only include them in Model C above if they are at least 80% complete, as the imputation of such variables is virtually impossible. If Model C is fitted, then we will also fit Model B2 on the same subset of participants (allowing comparison). If Model C is not fitted, Model B2 will not be either.

The data structure is strictly hierarchical (patients within NHS Talking Therapies services) and, therefore, the NHS Talking Therapies service will be treated as a random effect. We will estimate regression parameters using the method of maximum likelihood (MLE). Whilst restricted maximum likelihood estimation may result in less biased parameter estimates, it is uncertain whether this approach can be used in conjunction with probability weighting (see *Selection of Patients and Weighting*). However, given the large sample size (potentially 22 x 400 = 8,800), MLE will be approximately unbiased. We will also use an unstructured covariance matrix.

Missing data at follow-up: Dependent on the extent of missing data, the method of multiple imputation (MI) by chained equations will be employed, with the extent of missing data determining how many MI datasets will be generated (as a guide, one 'imputation' per 1% of missing data, but a minimum of 10). Imputation of missing 'follow-up' values will be done separately in each arm using, as a minimum, age, sex and the baseline values of both the PHQ-9 and the GAD-7. This will be our primary modelling approach (Model B1). As a sensitivity analysis, we will also conduct an analysis of complete cases (by which we mean where outcome data are missing for a particular patient at follow-up, we will assume that it is missing (completely) at random, and we will not replace it). Such patients will, therefore, be excluded from this analysis. No subgroup analyses are planned.

Alternative tests if distributional assumptions are violated: The distribution of the responses to the PHQ-9 and GAD-7 will be examined, prior to conducting the regression analyses, via a histogram and summary statistics. If the absolute value of the skewness exceeds 1 or the kurtosis falls outside the range 2 to 4, we will consider it to be non-normal and p-values will be validated using a non-parametric bootstrapped estimate of the standard error. A randomly generated seed will be used as a starting point for the bootstrapping process and 1,000 replications will be generated. One consideration here is that some statistical software does not permit bootstrapping in conjunction with probability weighting. If this is the case, it may be necessary to rely on the properties of large samples and assume that the sampling distribution of the mean is, in fact, normal (and that bootstrapping is not required). If the skewness is in a positive direction, we will also consider modelling a logarithmic transformation of the outcome. If a satisfactory transformation cannot be found, categorisation of the PHQ-9 and/ or GAD-7 will be considered.

The focus of our intervention will be on improving patient outcomes and engagement among those offered telephone treatments. However, there is a risk that our intervention will affect the types of patients who are offered telephone treatment in intervention sites, compared to controls. We will conduct a range of robustness checks to assess any potential impact, including exploring interview data with professionals to understand changes that might have been implemented and a comparison of the types of patient referred for telephone-treatment

before and after the intervention (via comparison of the baseline characteristics, such as depression/ anxiety severity, of patients in the intervention and usual care groups).

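### Drawing the anxiety sample only from patients left over after the depression sample under-represents patients with both conditions and can shrink the GAD-7 sample in smaller services

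*SAP*

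**What the plan says.** Under Selection of Patients and Weighting, the SAP sets the order of the draws: "The sample with depression will be drawn first and 400 patients who present to each NHS Talking Therapy service", with PHQ-9 of at least 5 at baseline. It continues: "A second, non-overlapping, random sample of 400 patients with anxiety will be selected to analyse this outcome", here with GAD-7 of at least 5. For shortfalls it says: "If there are fewer than 400 patients identified for either sample, all such patients will be retained".

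The primary approach uses weights, described as "deriving probability weights (the inverse of the probability of being selected", so that the sample better represents all patients seen by the team. Unweighted analyses are also planned. No weight formula is given for the second draw, and no reason is given for requiring the two samples to be disjoint.

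Under Sample Size and Power, at least 80% power with 22 clusters is conditional on at least 200 patients per provider and on the requirement that "the coefficient of variation in cluster size did not exceed 0.3". The section on patient selection then says, for PHQ-9 and GAD-7 alike, that 80% power survives the loss of half the outcomes. This presumes the full 400 per service.

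The only indication of service size is a minimisation factor: "Site size (count of NHS Talking Therapies patients receiving low-intensity therapy; <815 vs. ≥815". Of these cut-points the SAP says: "Minimisation factor dichotomies were chosen in order that groups would be of roughly equal size".

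**The concern.** A patient with both conditions can enter the GAD-7 sample only if the first draw missed them. A patient with GAD-7 of at least 5 and PHQ-9 below 5 is always available. The chance of selection for the GAD-7 analysis therefore differs between two kinds of patient within one service, and the gap widens as the service gets smaller.

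Two things are at stake. One is whom the GAD-7 effect describes, since the case mix now depends on service size. The other is sample size. Two disjoint samples of 400 need at least 800 distinct patients per service, and because depression is drawn first, any shortfall lands on anxiety. The fixed sample was introduced because cluster sizes varied more than expected, and for GAD-7 the non-overlap rule can bring that variation back.

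**Working it through.** **1. The plan's own power.** Inputs from the SAP: two-sided 5%, standardised difference 0.2, ICC 0.027, r = 0.5. Residual variance is 1 − 0.5² = 0.75. With k clusters per arm of mean size m:

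- design effect DE = 1 + ((1 + CV²)m − 1) × 0.027
- SE = √(2 × 0.75 × DE/(k m))
- power from the noncentral t with 2k − 2 df (normal approximation in brackets)

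Results:

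- 13 per arm, m = 100, CV 0: DE 3.673, SE 0.0651, power 83.8% (86.7%). The SAP says 84%.
- 11 per arm, m = 200, CV 0.3: DE 6.859, SE 0.0684, power 79.4% (83.3%). The SAP says at least 80%.
- 11 per arm, m = 400, CV 0: power 85.1% (88.4%).

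The plan's figures are reproduced to within a percentage point on the t version.

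**2. Share of patients with both conditions removed.** All of them have PHQ-9 of at least 5, so the first draw takes a share f = min(1, 400/D). This needs no prevalence assumption. To undo it, their weight relative to anxiety-only patients must be 1/(1 − f).

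| D | removed | relative weight needed |
|---|---|---|
| 400 or fewer | 100% | none exists |
| 450 | 89% | 9 |
| 500 | 80% | 5 |
| 815 | 49% | 1.96 |
| 1,000 | 40% | 1.67 |
| 2,000 | 20% | 1.25 |

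Removal of 90% or more needs D of at most 400/0.9 = 444.

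**3. Case mix within a service.** The SAP gives no prevalences, so two assumed sets follow (PHQ-9 ≥5 / GAD-7 ≥5 / both). The leftover pool is the anxiety-only patients plus (1 − f) × those with both. For example, at N = 500 with 90/90/85%: D = 450, 425 patients have both, 425 × (1 − 400/450) = 47 remain, 25 have anxiety only, so the pool is 72 and 65% of it has both.

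| N eligible | 90/90/85%: pool, share with both (true 94%) | 80/85/70%: pool, share with both (true 82%) |
|---|---|---|
| 400 | 20, 0% | 60, 0% |
| 500 | 72, 65% | 75, 0% |
| 815 | 356, 89% | 343, 64% |
| 2,000 | 1,422, 93% | 1,350, 78% |

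At N = 2,000 the pool exceeds 400, so 400 are sampled.

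**4. How many services.** This needs service sizes, which the SAP does not give. Assume 93/93/88% and lognormal sizes with median M. For D above 400 the pool is 0.93N − 0.88 × 400/0.93 = 0.93N − 378.5. It falls below 200 when N is under 622 and below 400 when N is under 837. The share of services under 200 is Φ(ln(622/M)/σ), with σ = √ln(1 + CV²), which is 0.472 for a CV of service size of 0.5 and 0.833 for 1.0.

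- M = 815: 28% (CV 0.5) to 37% (CV 1.0). By simulation of 22 services, the CV of the GAD-7 sample size is about 0.48 to 0.65.
- M = 1,500: 3% (CV 0.5) to 14% (CV 1.0). At CV 0.5 the sample-size CV is 0.13.
- M = 2,500: under 1% (CV 0.5) to 5% (CV 1.0).

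At M = 815, D is 400 or fewer when N is at most 400/0.93 = 430, which is 9% to 22% of services.

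**5. Power for GAD-7.** Suppose some of the 22 services yield about 35 anxiety patients (assumed) and the rest 400. With four such services, mean m = (4 × 35 + 18 × 400)/22 = 334 and CV is 0.42.

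| depleted services | CV | power, t (normal) |
|---|---|---|
| 2 | 0.29 | 82% (86%) |
| 4 | 0.42 | 79% (83%) |
| 6 | 0.54 | 75% (79%) |
| 11 | 0.84 | 63% (67%) |

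If half the outcomes are also missing, four depleted services give 76% (80%) and six give 72% (76%).

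**The case against.** The strongest case on the other side is that the effect is local and the evidence for its extent is thin.

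- **The GAD-7 result as a whole.** A reader might infer that it describes an atypical, largely non-depressed population. The figures do not support that. Depleted services contribute few patients: on the 93/93/88% assumption with M = 815, about 89% of the pooled unweighted sample still has both conditions, against a true 95%.
- **Weights.** A reader might infer that weighting can never repair the draw. Read literally, the inverse of the true selection probability includes (1 − 400/D) for patients with both conditions and restores the mix wherever D exceeds 400. That stands. But the SAP does not say the anxiety weight must reflect the first draw. Where all leftovers are kept, a weight based on the second draw alone is 1 and corrects nothing.
- **Service size.** The figure 815 counts patients receiving low-intensity therapy over an unstated period. The sampling pool is a different group over an unstated window, and the Inferential Analyses section thinks 22 × 400 = 8,800 patients possible. So a breach of the 200 and CV 0.3 conditions cannot be asserted as fact.
- **Bias between arms.** The rule is the same in both arms, and site size is minimised on and adjusted for. The SAP concedes that the intervention might change who is offered telephone treatment, which could alter D by arm, but nothing in the document shows that it does.
- **Visibility.** The Descriptive Analyses will report eligible and selected numbers per service, so depletion would be seen. Seeing it does not correct it.

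**Conclusion.** The mechanism follows directly from the SAP's text and holds at any prevalence. Patients with both conditions have zero chance of entering the GAD-7 sample where D is 400 or fewer, and a reduced chance everywhere else. Where D exceeds 400 the distortion is correctable, but only with a two-stage weight that the SAP does not define and that becomes extreme just above 400. The planned unweighted GAD-7 analyses are not corrected at all.

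The statement of 80% power for GAD-7 is weakened to a degree that depends on eligible counts the SAP does not give. It could be negligible if pools are mostly well above 1,500, and material if many services lie near or below 815. All case-mix, service-count and power-loss figures rest on assumed prevalences, sizes or yields; only the removal share 400/D does not.

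The PHQ-9 sample is drawn first and is untouched. This should be fixed, but it affects a secondary outcome and does not threaten the primary result.

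**What to change.** Delete the non-overlap requirement. Draw the GAD-7 sample independently, in each service, from all eligible patients with GAD-7 of at least 5, and let a patient appear in both samples. The selection probability is then min(1, 400/A) for every such patient, where A is the service's count with GAD-7 of at least 5, and the weight is its inverse. On the 90/90/85% assumption, a service of 400 would supply 360 anxiety patients, one of 500 would supply 400, and one of 815 would supply 400, each with the true 94% share of patients with both conditions.

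The cost is a change of wording and, if the second sample has already been drawn, a redraw from the same routine data. The PHQ-9 and GAD-7 results become correlated. This needs no correction, because they are fitted in separate models as primary and secondary outcomes.

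Analysing every patient with GAD-7 of at least 5 is not recommended, because it would bring back the cluster-size variation that the fixed sample was meant to remove.

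### Maximum likelihood is justified by 8,800 patients, but the arm comparison rests on 22 services, so the standard error is too small and the 5% error rate is not held

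*SAP*

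**What the plan says.** All references are to the SAP.

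- **Randomisation:** "allocation to either the intervention or usual care took place at the provider level, via minimisation". Four minimisation factors are listed, each split in two: recovery rate, site size, telephone use and deprivation.
- **Inferential Analyses, Analysis Method:** "Statistical tests will be performed with a 2-sided type I error rate of 5" per cent.
- **Inferential Analyses, Models to be fitted:** "All models will include the minimisation factors and the specified covariates as fixed effects". The arm coefficient is to be reported with its 95% confidence interval and p-value.
- **Inferential Analyses, text after the model table:** "the NHS Talking Therapies service will be treated as a random effect". Estimation is by ML. REML is acknowledged as possibly less biased but is set aside because "it is uncertain whether this approach can be used in conjunction with probability weighting". The choice is then defended: "However, given the large sample size (potentially 22 x 400 = 8,800), MLE will be approximately unbiased".
- **Selection of Patients and Weighting:** the primary approach uses inverse-probability-of-selection weights. Unweighted analyses are also planned.

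No degrees-of-freedom method, small-sample correction or reference distribution is named for the arm test.

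**The concern.** The difference between ML and REML that matters here lies in the between-service variance. How well that variance is estimated depends on the number of services and on how many service-level parameters are fitted, not on how many patients each service contributes. If 8,800 is treated as the relevant sample size, the ML variance and a large-sample test look harmless. With 22 services and several service-level covariates they are not.

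At stake are the confidence interval and p-value for the primary outcome (PHQ-9), and likewise for GAD-7. Both would be anti-conservative, and the 5% error rate that the SAP sets for itself would not be held.

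**Working it through.** **Inputs.** 22 services, ICC 0.027, baseline-endpoint correlation r = 0.5, standardised difference 0.2, at least 200 patients per service, coefficient of variation (CV) of cluster size up to 0.3 (Sample Size and Power). Service-level parameters: intercept + arm + four two-level minimisation factors = 6 (Randomisation; Models to be fitted). Residual service-level df: 22 - 6 = 16.

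**1. The SAP's own power figures.** With k services per arm and m patients per service, the variance factor is (1 - r²) × [1 + ((1 + CV²)m - 1) × ICC].
- 13 per arm, 100 patients, CV 0: design effect 1 + 99 × 0.027 = 3.673; effective n per arm 1300 / (0.75 × 3.673) = 471.9; noncentrality 0.2 × sqrt(471.9 / 2) = 3.072. Power is 83.8% with t on 24 df and 86.7% with z. The stated 84% matches the t calculation on cluster-level df.
- 11 per arm, 200 patients, CV 0.3: design effect 1 + (218 - 1) × 0.027 = 6.859; noncentrality 2.925. Power is 79.4% with t on 20 df and 83.3% with z. The stated minimum of 80% is met to rounding under t.

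So the design figure of 84% fits cluster-level df, while the rationale for the analysis appeals to the patient count.

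**2. Why more patients do not help.** The between-service share of the variance of a service mean is ICC / (ICC + (1 - ICC)/m).
- m = 200: 0.027 / (0.027 + 0.004865) = 85%.
- m = 400: 0.027 / (0.027 + 0.002433) = 92%.

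**3. Size of the understatement.** With equal cluster sizes, ML estimates the variance of a service mean as RSS/22, where RSS is the residual sum of squares of the service means; REML uses RSS/16. The standard-error ratio is sqrt(16/22) = 0.85, so the ML standard error is about 15% too small.

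**4. Two-sided type I error, closed form** (unweighted, complete data). The rate is P(|t16| > c × sqrt(16/22)), where c is the critical value used.

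| Analysis | Type I error |
|---|---|
| ML, Wald z (c = 1.96) | 11.4% |
| ML, likelihood-ratio test: P(\|t16\| > sqrt(16 × (exp(3.841/22) - 1))) | 10.0% |
| ML, t on 22 df | 9.6% |
| ML, t on 20 df | 9.4% |
| ML, t on 16 df | 8.9% |
| REML, z | 6.8% |
| REML, t on 16 df | 5.0% |

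By symmetry, the 11.4% splits into 5.7% in each direction, against a nominal 2.5%.

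**5. Sensitivity to the parameter count** (ML with z). Five service-level parameters give P(|t17| > 1.96 × sqrt(17/22)) = 10.3%. Two, with the minimisation factors left out, give P(|t20| > 1.96 × sqrt(20/22)) = 7.6%.

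**6. Simulation.** 6,000 trials per scenario, ICC 0.005 to 0.05, 200 to 400 patients per service, CV 0 to 0.3.
- ML with z: 10.9-11.7%
- Likelihood-ratio test: 9.4-10.3%
- ML with t16: 8.4-9.1%
- Uncorrected cluster-robust z: 10.1-11.6%
- REML with z: 6.3-7.1%
- REML with t16: 4.5-5.5%

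**7. Weights.** The SAP gives no service sizes, so the weights cannot be reconstructed. In a cluster-level check of an uncorrected robust z test, equal weights gave about 12%, and assumed weight CVs of 0.4 to 0.7 gave about 14-18%.

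**The case against.** The strongest defence is that the sentence in the SAP is about regression parameters, and for the arm coefficient it is right: ML is not a source of bias there. A reader might infer that the estimated treatment effect is biased, and the document does not support that. What stands against the SAP is that absence of bias in the coefficient says nothing about its standard error, and the interval and p-value depend on the standard error.

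Second, 11% is conditional. A reader might infer that the primary test as planned runs at 11%. The SAP does not allow so exact a statement: the primary analysis is weighted and multiply imputed, no reference distribution is named, and neither service sizes nor missingness are given. The direction does stand, since every unweighted ML variant tried exceeds 5%, and an uncorrected robust variance with weights does not rescue it.

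Third, the count of six could be questioned. Baseline Data describes patient-level deprivation linkage and commits only loosely to controlling for the service-level score, and the model table lists Model 0 with arm alone. Fewer service-level parameters reduce the inflation but do not remove it.

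Fourth, the bootstrap might be thought to cover the problem. Under the heading on alternative tests it applies only when the skewness or kurtosis limits are breached, and it may be dropped under weighting in favour of large-sample theory.

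Finally, a reader might infer that the weighted analysis should give way to an unweighted primary so that REML becomes available. Weighting is a deliberate choice, and because selection probability is constant within a service, removing the weights changes how much each service counts and may change the quantity estimated. The inference problem does not require that.

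**Conclusion.** Wrong as written. A patient count is used to dismiss a problem that depends on 22 services with about 6 service-level parameters. For unweighted, complete-data ML, the arm standard error is about 15% too small. The two-sided type I error is then about 11% with Wald z and about 9-10% with a t reference or likelihood-ratio test; with z it is still 7.6% if the minimisation factors were omitted. The stated rate is 5%.

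A reader might infer that a false finding of benefit is more than twice as likely as 5%. That sets a one-direction event against a two-sided rate. The like-for-like comparison is about 5.7% against 2.5%.

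The closed form assumes equal cluster sizes and normal service effects; the simulations relax the first. Weights and multiple imputation are outside all of these figures except the weight check, which rests on assumed weight variation.

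**What to change.** Delete the 8,800-patient justification and specify small-sample inference at service level for the primary arm effect.

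- **If weighting stays primary:** use a bias-corrected cluster-robust variance (CR2 or CR3 type), with a t reference on Satterthwaite df or on about 22 - 6 = 16 df. Check its performance under the actual weights, and state how it combines with multiple imputation.
- **For the unweighted analyses already planned:** use REML with Kenward-Roger or Satterthwaite df. REML alone is not enough, since with z it still gives about 6.8%.

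The unweighted model need not become primary.

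The cost is SAP wording, analysis options and a short performance check. Confidence intervals become wider. Power at 200 patients per service and CV 0.3 is about 78% on 16 df, against 79% on 20 df, with no credit for between-service variance explained by the minimisation factors.
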